12.3. Appendix 3 Genetic Research

Genetics – Background

Naturally occurring genetic variation may contribute to inter-individual variability in response to medicines, as well as an individual's risk of developing specific diseases. Genetic factors associated with disease characteristics may also be associated with response to therapy, and could help to explain some clinical study outcomes. For example, genetic variants associated with age-related macular degeneration (AMD) are reported to account for much of the risk for the condition [Gorin 2012] with certain variants reported to influence treatment response [Chen 2012]. Thus, knowledge of the genetic etiology of disease may better inform understanding of disease and the development of medicines. Additionally, genetic variability may impact the pharmacokinetics (absorption, distribution, metabolism, and elimination), or pharmacodynamics (relationship between concentration and pharmacologic effects or the time course of pharmacologic effects) of a specific medicine and/or clinical outcomes (efficacy and/or safety) observed in a clinical study.

Genetic Research Objectives and Analyses

The objectives of the genetic research are to investigate the relationship between genetic variants and:

- Response to medicine or any concomitant medicines;
- Asthma susceptibility, severity, and progression and related conditions

Genetic data may be generated while the study is underway or following completion of the study. Genetic evaluations may include focused candidate gene approaches and/or examination of a large number of genetic variants throughout the genome (whole genome analyses). Genetic analyses will utilize data collected in the study and will be limited to understanding the objectives highlighted above. Analyses may be performed using data from multiple clinical studies to investigate these research objectives.

Appropriate descriptive and/or statistical analysis methods will be used. A detailed description of any planned analyses will be documented in a Reporting and Analysis Plan (RAP) prior to initiation of the analysis. Planned analyses and results of genetic investigations will be reported either as part of the clinical RAP and study report, or in a separate genetics RAP and report, as appropriate.

Study Population

Any subject who is enrolled in the study can participate in genetic research. Any subject who has received an allogeneic bone marrow transplant must be excluded from the genetic research.

Study Assessments and Procedures

A key component of successful genetic research is the collection of samples during clinical studies. Collection of samples, even when no *a priori* hypothesis has been

identified, may enable future genetic analyses to be conducted to help understand variability in disease and medicine response.

- A 6ml blood sample will be taken for Deoxyribonucleic acid (DNA) extraction. A blood sample is collected at the baseline visit, after the subject has been randomized and provided informed consent for genetic research. Instructions for collection and shipping of the genetic sample are described in the laboratory manual. The DNA from the blood sample may undergo quality control analyses to confirm the integrity of the sample. If there are concerns regarding the quality of the sample, then the sample may be destroyed. The blood sample is taken on a single occasion unless a duplicate sample is required due to an inability to utilize the original sample.

The genetic sample is labelled (or “coded”) with the same study specific number used to label other samples and data in the study. This number can be traced or linked back to the subject by the Investigator or site staff. Coded samples do not carry personal identifiers (such as name or social security number).

Samples will be stored securely and may be kept for up to 15 years after the last subject completes the study, or GSK may destroy the samples sooner. GSK or those working with GSK (for example, other researchers) will only use samples collected from the study for the purpose stated in this protocol and in the informed consent form. Samples may be used as part of the development of a companion diagnostic to support the GSK medicinal product.

Subjects can request their sample to be destroyed at any time.

Informed Consent

Subjects who do not wish to participate in the genetic research may still participate in the study. Genetic informed consent must be obtained prior to any blood being taken.

Subject Withdrawal from Study

If a subject who has consented to participate in genetic research withdraws from the clinical study for any reason other than being lost to follow-up, the subject will be given a choice of one of the following options concerning the genetic sample, if already collected:

- Continue to participate in the genetic research in which case the genetic DNA sample is retained
- Discontinue participation in the genetic research and destroy the genetic DNA sample

If a subject withdraws consent for genetic research or requests sample destruction for any reason, the Investigator must complete the appropriate documentation to request sample destruction within the timeframe specified by GSK and maintain the documentation in the site study records.

Genotype data may be generated during the study or after completion of the study and may be analyzed during the study or stored for future analysis.

- If a subject withdraws consent for genetic research and genotype data has not been analyzed, it will not be analyzed or used for future research.
- Genetic data that has been analyzed at the time of withdrawn consent will continue to be stored and used, as appropriate.

Screen and Baseline Failures

If a sample for genetic research has been collected and it is determined that the subject does not meet the entry criteria for participation in the study, then the Investigator should instruct the subject that their genetic sample will be destroyed. No forms are required to complete this process as it will be completed as part of the consent and sample reconciliation process. In this instance a sample destruction form will not be available to include in the site files.

Provision of Study Results and Confidentiality of Subject's Genetic Data

GSK may summarize the genetic research results in the clinical study report, or separately and may publish the results in scientific journals.

GSK may share genetic research data with other scientists to further scientific understanding in alignment with the informed consent. GSK does not inform the subject, family members, insurers, or employers of individual genotyping results that are not known to be relevant to the subject's medical care at the time of the study, unless required by law. This is due to the fact that the information generated from genetic studies is generally preliminary in nature, and therefore the significance and scientific validity of the results are undetermined. Further, data generated in a research laboratory may not meet regulatory requirements for inclusion in clinical care.

References

12.4.1. Definition of Adverse Events

Adverse Event Definition:

- An AE is any untoward medical occurrence in a patient or clinical investigation subject, temporally associated with the use of a medicinal product, whether or not considered related to the medicinal product.
- NOTE: An AE can therefore be any unfavorable and unintended sign (including an abnormal laboratory finding), symptom, or disease (new or exacerbated) temporally associated with the use of a medicinal product.

Events meeting AE definition include:

- Any abnormal laboratory test results (hematology, clinical chemistry, or urinalysis) or other safety assessments (e.g., ECGs, radiological scans, vital signs measurements), including those that worsen from baseline, and felt to be clinically significant in the medical and scientific judgement of the Investigator.
- Exacerbation of a chronic or intermittent pre-existing condition including either an increase in frequency and/or intensity of the condition.
- New conditions detected or diagnosed after study treatment administration even though it may have been present prior to the start of the study.
- Signs, symptoms, or the clinical sequelae of a suspected interaction.
- Signs, symptoms, or the clinical sequelae of a suspected overdose of either study treatment or a concomitant medication (overdose per se will not be reported as an AE/SAE unless this is an intentional overdose taken with possible suicidal/self-harming intent. This should be reported regardless of sequelae).
- "Lack of efficacy" or "failure of expected pharmacological action" per se will not be reported as an AE or SAE. However, the signs and symptoms and/or clinical sequelae resulting from lack of efficacy will be reported if they fulfil the definition of an AE or SAE.

Events NOT meeting definition of an AE include:

- Any clinically significant abnormal laboratory findings or other abnormal safety assessments which are associated with the underlying disease, unless judged by the Investigator to be more severe than expected for the subject's condition.
- The disease/disorder being studied or expected progression, signs, or symptoms of the disease/disorder being studied, unless more severe than expected for the subject's condition.
- Medical or surgical procedure (e.g., endoscopy, appendectomy): the condition that

leads to the procedure is an AE.

- Situations where an untoward medical occurrence did not occur (social and/or convenience admission to a hospital).
- Anticipated day-to-day fluctuations of pre-existing disease(s) or condition(s) present or detected at the start of the study that do not worsen.

12.4.2. Definition of Serious Adverse Events

If an event is not an AE per definition above, then it cannot be an SAE even if serious conditions are met (e.g., hospitalization for signs/symptoms of the disease under study, death due to progression of disease, etc).

Serious Adverse Event (SAE) is defined as any untoward medical occurrence that, at any dose:

a. Results in death

b. Is life-threatening

NOTE:

The term 'life-threatening' in the definition of 'serious' refers to an event in which the subject was at risk of death at the time of the event. It does not refer to an event, which hypothetically might have caused death, if it were more severe.

c. Requires hospitalization or prolongation of existing hospitalization

NOTE:

- In general, hospitalization signifies that the subject has been detained (usually involving at least an overnight stay) at the hospital or emergency ward for observation and/or treatment that would not have been appropriate in the physician's office or out-patient setting. Complications that occur during hospitalization are AEs. If a complication prolongs hospitalization or fulfills any other serious criteria, the event is serious. When in doubt as to whether "hospitalization" occurred or was necessary, the AE should be considered serious.
- Hospitalization for elective treatment of a pre-existing condition that did not worsen from baseline is not considered an AE.

d. Results in disability/incapacity

NOTE:

- The term disability means a substantial disruption of a person's ability to conduct normal life functions.
- This definition is not intended to include experiences of relatively minor medical significance such as uncomplicated headache, nausea, vomiting, diarrhea, influenza, and accidental trauma (e.g. sprained ankle) which may interfere or prevent everyday life functions but do not constitute a substantial disruption

e. Is a congenital anomaly/birth defect


f. Other situations:
 
 • Medical or scientific judgment should be exercised in deciding whether reporting is appropriate in other situations, such as important medical events that may not be immediately life-threatening or result in death or hospitalization but may jeopardize the subject or may require medical or surgical intervention to prevent one of the other outcomes listed in the above definition. These should also be considered serious. • Examples of such events are invasive or malignant cancers, intensive treatment in an emergency room or at home for allergic bronchospasm, blood dyscrasias or convulsions that do not result in hospitalization, or development of drug dependency or drug abuse

g. Is associated with liver injury and impaired liver function defined as:
 
 • ALT \geq 3xULN and total bilirubin* \geq 2xULN (>35% direct), or • ALT \geq 3xULN and INR** > 1.5. 
* Serum bilirubin fractionation should be performed if testing is available; if unavailable, measure urinary bilirubin via dipstick. If fractionation is unavailable and ALT \geq 3xULN and total bilirubin \geq 2xULN, then the event is still to be reported as an SAE.
 
** INR testing not required per protocol and the threshold value does not apply to subjects receiving anticoagulants. If INR measurement is obtained, the value is to be recorded on the SAE form.

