7.3.6. Asthma Exacerbations

For the purposes of this study, moderate/severe asthma exacerbations will be collected and recorded on the asthma exacerbation eCRF page from the start of randomized double blinded treatment until Visit 8/EOS Visit or the Early Withdrawal Visit for those subjects

that withdraw from participation in the study (see Section 5.6). Moderate/severe asthma exacerbations should not be recorded as an adverse event unless:

- They meet the definition of an Adverse Event (see Appendix 4) and occur:
 - After the start of study treatment until the start of double blinded study treatment or;
 - After completion of the Visit 8/EOS Visit (or Early Withdrawal Visit) assessments until the follow-up contact.

OR

- They meet the definition of a Serious Adverse Event (see Appendix 4).
Note: The SAE page of the eCRF should be completed in addition to the asthma exacerbation eCRF page if the exacerbation occurs after the start of double blinded treatment but before completion of the Visit 8/EOS Visit or Early Withdrawal Visit assessments.

For consistency, exacerbations separated by less than 7 days will be treated as a continuation of the same exacerbation.

Alerts will be programmed into the eDiary to instruct the subject to contact the Investigator immediately for a medical assessment (see Section 7.3.5.1.6). The notification of decreasing asthma control from the eDiary will assist the Investigator in the identification of new asthma exacerbations.

Subjects will also complete a paper Medical Problems/Medications Taken worksheet to record medical problems experienced and medications used during the study, as well as all emergency department visits and/or hospitalizations that occur during their participation in the study. This paper worksheet must be reviewed by the Investigator (or designee) at each visit to the study site to assist the Investigator in the identification of new asthma exacerbations.

All moderate/severe asthma exacerbations will be recorded in the eCRF by the Investigator (or designee).

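### Do Protocol Sections 7.3.6, 12.4.1 and 12.4.2 conflict on whether a hospitalized asthma exacerbation is an SAE?

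*Protocol*

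**What the plan says.** Section 7.3.6 sends moderate and severe exacerbations to a dedicated eCRF page from the start of randomized treatment until Visit 8/EOS or the Early Withdrawal Visit. On the AE side it says: "Moderate/severe asthma exacerbations should not be recorded as an adverse event unless" one of two conditions holds. Either the event meets the AE definition and falls before double-blind treatment or after the final visit, or it meets the Appendix 4 definition of an SAE. For SAEs inside the double-blind window a Note adds: "The SAE page of the eCRF should be completed in addition to the asthma exacerbation eCRF page".

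Appendix 4 supplies the definitions. Section 12.4.1 counts as an AE any "disease (new or exacerbated) temporally associated with the use of a medicinal product", and lists among qualifying events "Exacerbation of a chronic or intermittent pre-existing condition including either an increase in frequency and/or intensity of the condition". Among events that do not qualify it lists "The disease/disorder being studied or expected progression, signs, or symptoms of the disease/disorder being studied, unless more severe than expected" for that subject. Section 12.4.2 makes hospitalization a seriousness criterion (item c), but begins with the sentence "If an event is not an AE per definition above, then it cannot be an SAE even if serious conditions are met (e.g., hospitalization", whose parenthesis reads "hospitalization for signs/symptoms of the disease under study, death due to progression of disease, etc". Item f gives "intensive treatment in an emergency room or at home for allergic bronchospasm" as one illustration of an important medical event.

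**The concern.** Take one event: an exacerbation during double-blind treatment that leads to admission. One investigator treats it as an exacerbation of a pre-existing condition, hence an AE, serious because of the admission, and completes the SAE page. Another treats it as the disease under study, no worse than expected, sees the 12.4.2 example and completes the exacerbation page only.

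During double-blind treatment, meeting the SAE definition is the only route by which an exacerbation reaches the AE/SAE pages. The second investigator's case would therefore miss 24-hour reporting (Section 7.5.1.1), the SAE tables, and the special-interest group for asthma-related intubations and deaths, which SAP Section 8.3 builds from coded AE terms. Uneven practice between sites would make those asthma entries hard to interpret.

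**Working it through.** No sample size, power or error-rate figure depends on this, so the check is to read the passages together.

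**1. What the 12.4.2 sentence decides.** It is a conditional: if an event is not an AE, meeting a seriousness criterion does not make it an SAE. The parenthesis illustrates seriousness that cannot rescue a non-AE. It does not say that an asthma admission is a non-AE; that question goes back to 12.4.1.

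**2. What 12.4.1 decides.** The exclusion for the disease under study is lifted when the event is more severe than expected for the subject. That is a judgment for the investigator, like others in Appendix 4. The entry criteria do not make an admission expected: Section 5.1, criterion 4, is met by a documented healthcare contact, or by a temporary therapy change under an action plan, in the prior year.

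**3. What 7.3.6 adds, by period.**

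| Period | Recording under Section 7.3.6 |
|---|---|
| Study treatment before double-blind start | AE if the AE definition is met; SAE if the SAE definition is met |
| Double-blind start to EOS/EW visit | Exacerbation page; SAE page as well if the SAE definition is met |
| After EOS/EW visit to follow-up contact | AE if the AE definition is met; SAE if the SAE definition is met |

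If the 12.4.2 example were a blanket exclusion of asthma admissions and deaths, the SAE branch of 7.3.6 and its Note would have almost nothing to cover. The reading that gives every passage work to do is the conditional one. The bronchospasm example in item f does not settle the matter either way: it sits in a general list with cancers, blood dyscrasias and convulsions, and concerns events that may not lead to admission.

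**4. What is recorded whatever the SAE decision.**
- Every moderate or severe exacerbation up to EOS/EW, including after treatment is stopped (Section 7.3.6). The key secondary analysis uses on- and post-treatment events (SAP Section 7.2.6).
- Exacerbations needing hospitalization, an emergency visit or systemic corticosteroids, summarized under SAP Section 7.2.5, with exacerbations listed in Listings 16 and 17.
- Asthma-related hospitalizations and emergency visits, as healthcare utilization (Section 7.3.3.5).
- All deaths, on a dedicated page (Section 7.5.1.4.2) and in patient profiles (SAP Listing 74).

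**5. Between-arm effect.** Suppose a share *p* of hospitalized exacerbations is filed as SAEs, and assume *p* is the same in two arms because investigators are blinded. With true counts N1 and N2, the reported counts are *p*N1 and *p*N2. Their ratio is still N1/N2, while their difference shrinks by the factor *p*. Counts could be understated, but no direction of bias in the ratio follows.

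**The case for a change.** The strongest reply is that allowing the right answer is not the same as producing consistent answers. Section 7.3.6 defers to Appendix 4, which gives no threshold for more severe than expected in asthma. Subjects enter with inadequately controlled disease and recent acute symptoms, so an investigator could reasonably call an exacerbation expected. The when-in-doubt sentence in 12.4.2 covers doubt about whether hospitalization occurred or was necessary, not doubt about AE status. The other records preserve the facts, but none of them triggers 24-hour reporting or feeds the AE-coded tables, and the documents describe no cross-check of hospitalized exacerbations against SAE pages. After the final visit the exacerbation page is no longer used. Follow-up contact comes 6 to 11 days later (7 days, window -1/+4), and AE recording in that stretch rests on the same judgment.

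Much of this stands as a description. The example is awkward in an asthma trial, a site could misread it, and SAE counts for asthma could vary between sites. It does not show a stated rule giving a wrong result. Relying on investigator judgment is the chosen rule, and a request for asthma-specific guidance is a request for more detail. The gap after the final visit is short, Section 7.3.6 covers it with an AE route, and medication taken for an exacerbation then is still recorded (Section 6.9).

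**Conclusion.** The concern does not hold as a conflict, and no change to the plan follows. The three sections can be applied together: 12.4.1 decides AE status by investigator judgment, 12.4.2 decides seriousness for events that pass, and 7.3.6 says which pages to complete in each period. The remaining ambiguity is one that ordinary site guidance on SAE reporting can handle.

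The effect on the primary and key secondary endpoints is nil, because neither uses SAE status. The effect on asthma SAE counts and the asthma/bronchospasm special-interest group cannot be sized, since the documents give neither an admission rate nor a misclassification rate. The conclusion rests on two assumptions: that investigators read the 12.4.2 sentence as the conditional it is, and that exacerbations reach their own eCRF page as Section 7.3.6 requires. If the first fails at some sites, an on-study asthma admission or death is still visible in the exacerbation, healthcare-utilization or death records, though those records would not supply the missing 24-hour report.

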12.4.3. Definition of Cardiovascular Events

Cardiovascular Events (CV) Definition:

Investigators will be required to fill out the specific CV event page of the CRF for the following AEs and SAEs:
 
 • Myocardial infarction/unstable angina • Congestive heart failure • Arrhythmias • Valvulopathy • Pulmonary hypertension • Cerebrovascular events/stroke and transient ischemic attack • Peripheral arterial thromboembolism • Deep venous thrombosis/pulmonary embolism • Revascularization

12.4.4. Recording of AEs and SAEs

AEs and SAE Recording:

- When an AE/SAE occurs, it is the responsibility of the Investigator to review all documentation (e.g., hospital progress notes, laboratory, and diagnostics reports) relative to the event.
- The Investigator will then record all relevant information regarding an AE/SAE in the CRF
- It is **not** acceptable for the Investigator to send photocopies of the subject's medical records to GSK in lieu of completion of the GSK, AE/SAE CRF page.
- There may be instances when copies of medical records for certain cases are requested by GSK. In this instance, all subject identifiers, with the exception of the subject number, will be blinded on the copies of the medical records prior to submission of to GSK.
- The Investigator will attempt to establish a diagnosis of the event based on signs, symptoms, and/or other clinical information. In such cases, the diagnosis will be documented as the AE/SAE and not the individual signs/symptoms.
- Subject-completed Value Evidence and Outcomes questionnaires and the collection of AE data are independent components of the study.
- Responses to each question in the Value Evidence and Outcomes questionnaire will be treated in accordance with standard scoring and statistical procedures detailed by the scale's developer.
- The use of a single question from a multidimensional health survey to designate a cause-effect relationship to an AE is inappropriate.

